8.4.4 Appropriateness of safety measurements

Pulmonary function and status are monitored by assessments, including spirometry, DLCO, **CCI** 6MWT, and PROs amongst others, which are detailed under the efficacy measures in the study. Cohort specific safety assessments are detailed in [Section 17](#).

Further safety assessments (e.g. hematology, serum chemistry, coagulation, ECGs, vital signs, physical exams) are standard for investigations monitoring general safety in phase 2 clinical trials.

8.5 Additional assessments

8.5.1 Clinical Outcome Assessments (COAs)

As per [Section 4.6](#), during a Public Health Emergency as declared by Local or Regional authorities (i.e. pandemic, epidemic, or natural disaster), that limits or prevents on-site study visits, COA data may be collected remotely.

Patient reported outcomes (PRO)

The participant must be given the PRO measure(s) to be completed at the scheduled visit before 6MWT. Participant's refusal to complete all or any part of a PRO measure should be documented in the study data capture system and should be captured as a protocol deviation. Handling of protocol deviations can be modified if needed per study protocol.

Participant questionnaires should be completed in the language most familiar to the participant.

If self-administered:

The participant should be given sufficient space and time to complete the PRO measure(s).

The site personnel should check PRO measure(s) for completeness and ask the participant to complete any missing responses.

8.5.1.1 Leicester Cough Questionnaire

The Leicester Cough Questionnaire (LCQ) is a 19-item chronic cough/respiratory-specific measure designed to assess the impact of chronic cough on health-related quality of life (HRQoL), using a recall period of the last 24 hours. It can be completed in less than 5 minutes.

8.5.1.2 Living with IPF (Impacts and Symptoms Modules)

Living with IPF (L-IPF) is a tool that assesses symptoms and impacts of IPF. The Symptoms Module consists of 20 questions. This module is designed to assess symptoms experienced from IPF over the last 24 hours. The symptoms questions are in relation to physical activities, cough, and energy level. The last 5 questions are regarding supplemental oxygen use. The Impacts Module consists of 20 questions on how IPF affects quality of life over the last 7 days.

8.5.1.3 K-BILD

The King's Brief Interstitial Lung Disease (K-BILD) is a 15-item HRQOL questionnaire. The K-BILD questionnaire assesses 3 domains (breathlessness/activities, psychological and chest symptoms) with a 2-week recall.

8.5.1.4 Raghu Scale for Pulmonary Fibrosis

The Raghu-Scale for Pulmonary Fibrosis (R-Scale for PF) is a questionnaire designed to assess the impact of lung disease on quality of life. R-Scale for PF consists of 5 questions with a 2-week recall.

8.5.2 Pharmacokinetics

PK samples will be collected at the visits defined in [Section 17](#).

8.5.3 Biomarkers

The biomarkers selected in this study may explore the potential mechanism of action, pharmacodynamics, and safety responses to the drug treatment. The biomarker strategy may enhance our understanding of the mechanism of the compound on inflammation and fibrosis in humans with IPF disease. The pharmacogenetic assessment will be performed to examine the association of genetic variances related to drug response and metabolism. The timing and details of the samples collected are defined in the PK/PD and Biomarker Assessment Schedule in [Section 17](#). Serum and plasma biomarkers will be collected, stored, and banked for future testing.

Exploratory Biomarkers

Serum and plasma samples will be collected for exploratory disease related biomarker analysis. Additional samples for biomarkers will be collected, banked, and stored.

Protein profiling of blood samples may be analyzed in multiplex, hypothesis-free platforms to study protein biomarkers.

Samples will be collected at the time points defined in the PK/PD and Biomarker Assessment Schedule ([Section 17](#)). The list may be changed or expanded further, as it is recognized that more relevant or novel biomarkers may be discovered during the conduct of

the study. Follow instructions for sample collection, numbering, processing, and shipment provided in the laboratory manual.

Descriptions of the assays, platforms, and technologies to be used in the exploratory biomarker evaluations will be included in the associated bioanalytical data reports. Clinical samples for the assessment of exploratory biomarkers may be stored and their processing and analysis conditioned to the decisions to be made based on overall study outcome and/or future scientific needs. Exploratory biomarker samples remaining after analyses may be stored for up to 15 years to address additional relevant scientific questions.

To assess the impact of the drug on disease related biomarkers; markers may include but not limited to:

CCI [REDACTED]

CCI [REDACTED]

CCI [REDACTED]

CCI [REDACTED]

CCI [REDACTED]

CCI [REDACTED]

Samples will be collected at the time point defined in the Assessment schedule ([Section 17](#)).

Detailed instructions for sample collection, numbering, processing, and shipment will be provided in the Central Lab Manual.

DNA sampling / Pharmacogenetics

Exploratory DNA Sampling (Optional)

The study includes an optional genetic research component which requires a separate informed consent signature if the participant agrees to participate. As permitted by local governing regulations and by IRB/EC, it is required as part of this protocol that the investigator presents these options to the participant.

The purpose of genetic research may be to better understand the safety and efficacy of treatment, or to learn more about human diseases, or to help develop ways to detect, monitor and treat diseases.

As technology changes over time, the most appropriate technology will be used at the time the exploratory genetic research is performed. This may include the study of the entire genome.

Sample(s) will be collected at the time point(s) defined in the PK/PD and Biomarker Assessment Schedule ([Section 17](#)).

[figure not shown]
Laboratory manuals will be provided with detailed information on sample collection, handling, and shipment.

DNA samples

The use of DNA to search for biomarkers of disease and drug action is exploratory. Any results from this DNA study will not be placed in the participant's medical records.

To maximize confidentiality, all samples will be double coded to prevent the exposure of the participant's information and identity. This double-coding process allows Novartis to go back and destroy the sample at the participant's request. In addition, sample information is stored in one secured database while genetic data is stored in an independent secured database.

8.5.3.1 CCI

8.5.3.2 Use of residual biological samples

Residual blood, serum, and plasma samples may be used for another protocol specified endpoint. Any residual samples remaining after the protocol-defined analyses have been performed may be used for additional exploratory analyses. This may include but is not limited to using residual samples for protein binding, metabolite profiling or quantification, biomarkers of transporters or metabolic enzyme activity or other bioanalytical purposes (e.g. cross check between different sites and/or stability assessment). The results from these exploratory analyses may not necessarily be included in the clinical study report.

8.5.4 Immunogenicity

Immunogenicity samples may be obtained in cohorts where the IP is thought to have the potential to elicit an immunogenic reaction, including the placebo groups in those cohorts.

In case of suspected allergic hypersensitivity, the participant should return to the site and a sample to assess immunogenicity will be collected.

In case of positive immunogenicity, backup of previous pre-dose PK samples could be used to better characterize the onset of immunogenicity response.

Follow instructions outlined in the laboratory manual regarding sample collection, numbering, processing, and shipment.

Please refer to [Section 17](#).

Immunogenicity analytical method(s)

A validated ligand binding assay (i.e. ELISA, MSD, etc.) will be used for the detection of potential antibodies per [Section 17](#). Confirmed immunogenicity positive samples will be further analyzed for presence of neutralizing antibodies using a validated method.

The detailed methods for immunogenicity assessment will be described in the Bioanalytical Data Report.

9 Discontinuation and completion

9.1 Discontinuation from study treatment and from study

9.1.1 Discontinuation from study treatment

Discontinuation of study treatment for a participant occurs when study treatment is permanently stopped for any reason (prior to the planned completion of study drug administration) and can be initiated by either the participant or the investigator.

The investigator must discontinue study treatment for a given participant if he/she believes that continuation would negatively impact the participant's well-being.

Participants who discontinue study treatment must return for an Early End of Treatment visit as soon as possible, but within 4 weeks after discontinuation of treatment. All assessments planned for the Day 183 visit will be performed. HRCT will only be done if discontinuation occurs after Day 85. If the End of Treatment visit occurs in the visit window for the next scheduled visit, then the scheduled visit may serve as the Early End of Treatment visit, and all assessments for the End of Treatment visit should occur at that time. Participants will go on to complete all remaining visits as scheduled, including the Day 183 visit and Safety Follow-up visit (see [Table 8-1](#) for a list of assessments to occur at the End of Treatment and Safety Follow-Up visits). For participants who continue scheduled visits, the HRCT scan will be performed as scheduled at the Day 183 visit.

Discontinuation from study treatment is required under the following circumstances:

- Participant/guardian decision
- The participant becomes pregnant. Study treatment must be discontinued immediately. Report the pregnancy according to instructions in [Section 10.1.4](#)
- If organ transplantation becomes necessary during the study treatment
- The participant is unwilling or unable to comply with the protocol
- Adverse event that puts the participant at risk if continuation on investigational product or in the study, at the discretion of the investigator.
- If a liver or renal event occurs, follow guidelines outlined in [Section 16.1](#) (Appendix 1) and [Section 16.2](#) (Appendix 2), respectively, regarding discontinuation of study treatment.

If discontinuation from study treatment occurs, the investigator should make a reasonable effort to understand the primary reason for the participant's discontinuation from study treatment and record this information.

After discontinuation from study treatment, at a minimum the following data should be collected at clinic visits or via telephone/email contact:

- New / concomitant treatments
- Adverse Events / Serious Adverse Events

The investigator must also contact the IRT to register the participant's discontinuation from study treatment.

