4.5 Risks and benefits

The risk to participants in this trial may be minimized by compliance with the eligibility criteria and study procedures, as well as close clinical monitoring. Refer to the Investigator's Brochure of each respective investigational product as identified per cohort.

Women of child-bearing potential and sexually active males must be informed that taking the study treatment may involve unknown risks to the fetus if pregnancy were to occur during the study and agree that in order to participate in the study they must adhere to the contraception requirements outlined in the exclusion criteria.

Detailed descriptions of the expected safety and tolerability characteristics of each IP can be found in [Section 17](#).

The key risks associated with participation in CADPT09A12201, and their mitigation include:

1. Two HRCTs will be performed in this study. Published dosimetry for HRCT shows a total maximal amount of radiation exposure per participant in the study will be approximately 10 mSv (1000 mrem), less than the annual limits allowed in the EU and US, 20 and 50 mSv, respectively. This amount of radiation is equivalent to approximately 3-5 years of exposure to background radiation (9 to 15 mSv, average yearly background dose is approximately 3 mSv in the US). For effective radiation doses between 3 mSv (300 mrem) and 50 mSv (5000 mrem), the risk is considered to be minimal. The radiation exposure in this study is aligned with other IRB approved respiratory trials, involves minimal risk, and is necessary to obtain the desired research information.
2. Although this study excludes participants who are <40 years of age, there is a potential for enrolling women of childbearing potential and the treatments may involve unknown risks to the fetus if pregnancy were to occur during the study. This risk is mitigated by requiring proof the participant is not pregnant prior to start of treatment and requiring appropriate contraception during and for a suitable interval after treatment, as defined for each IP. See [Section 17](#) for further details on each IP.

Based on the above risk considerations, additional safety measures employed in CADPT09A12201 include, but are not limited to:

- The study employs safety management measures, which are considered relevant and appropriate for this participant population and protocol to facilitate safe conduct of the study.

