All assessments planned for the Day 183 visit except for the HRCT scan will be performed (see [Section 9.1.1](#) for details). If a subject is withdrawn from the study prior to the end of the Treatment Period, an Early EoT visit will occur as soon as possible, but within 4 weeks. All assessments planned for the Day 183 visit will be performed except HRCT. If early EoT falls on or after Day 85 visit, HRCT should also be performed (see [Section 9.1.2](#) for details).

² To be reconfirmed at randomization

³ As required. Women of childbearing potential must have serum pregnancy test at screening and this test must be performed within 7 days prior to dosing.

Subsequent testing may be urine (see [Section 8.4](#) Safety for additional information).

⁴ See [Section 17](#) for additional cohort assessments, if needed

⁵ Cardiac and Pulmonary exams must be performed. Symptom driven for all other organ systems

⁶ ECG and DLCO will be performed using local site equipment

⁷ Spirometry at screening visit will include Bronchodilator response.

⁸ The 6MWT must be performed after all ECGs, PFTs and PROs have been completed. Each 6MWT consists of 2 separate walks.

⁹ See [Section 17](#) for specific assessments

¹⁰ PK samples may be collected at unscheduled times

¹¹ See [Section 17](#) for specific time point for study drug arm

¹² Genetic research ICF must be obtained before optional DNA sampling. This optional sample can be collected anytime on Day 1 visit or thereafter.

¹³ See [Section 17](#) for study drug administration

¹⁴ Impacts and Symptoms Modules

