8.3.4 High Resolution CT of Chest

High Resolution Computed Tomography (HRCT) will be performed at screening (which will be used as the baseline measure) and at Week 26. At the time points specified in the schedule, an HRCT scan of the lung, without contrast agent, will be acquired. The acquisition will include inspiratory and expiratory image sets at both assessment time points. In all participants within the study, the baseline and follow-up HRCT scan should be performed where possible on the same scanner. Protocol specific requirements of the HRCT and machine settings are provided to all sites as part of a separate Imaging Manual. Additionally, the imaging vendor will provide centralized review of the HRCT scans. The methods for assessment and recording are specified in the Imaging Review Charter.

In summary, evaluation of the HRCT scans may be used to assess extent of:

- Lung parenchymal classification analysis and valuation of change from baseline compared to week 26 of HRCT
 - Percent of lung or regional volume which constitutes normal lung tissue, areas of low attenuation (LAA), ground-glass opacity, reticulation, honey-combing, and composites of these indices.

HRCT involves exposure to radiation. The total amount of radiation for acquisition at baseline and Week 26 of HRCT scans will be optimized to be within the annual limits of exposure defined in both EU and NA guidelines. The total radiation received in this study is equivalent to approximately 3-5 years of normal radiation received in everyday life. This amount of radiation is considered to be a minor to intermediate risk and is necessary to obtain the research information desired.

Note: The coded medical images will be used primarily for analysis as described in this protocol; however, the images may also be used for the development and evaluation of new analysis methods directly related to the area of research that this study covers.

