9.1.2 Discontinuation from study

Discontinuation from study is when the participant permanently stops receiving the study treatment, and further protocol-required assessments or follow-up, for any reason.

If a participant is discontinued from the study, an Early End of Treatment visit will be scheduled or performed as soon as possible but within 4 weeks. All assessments planned for the Day 183 visit will be performed except HRCT. If early EOT falls on or after Day 85 visit, HRCT should also be performed (see [Table 8-1](#) for a list of assessments to occur at the End of Treatment visit).

If a participant is unwilling or unable to attend, at the minimum, the End of Treatment visit, and decides to withdraw from the study, the reason for withdrawal will be documented and no further assessments will be obtained.

Please note, if a participant decides to discontinue from the study, a withdrawal of consent should NOT be completed unless the participant meets the particular criteria noted in [Section 9.2](#).

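### Protocol 9.1.1 and Table 8-1 footnote 1 disagree on the early HRCT after stopping treatment; read literally, 9.1.1 gives three scans where 4.5 states two

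*Protocol*

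**What the plan says.** Three parts of the protocol bear on a participant who permanently stops treatment but remains in the study.

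- **Section 9.1.1** requires an early End of Treatment (EOT) visit within 4 weeks, with the Day 183 assessments. On imaging it says "HRCT will only be done if discontinuation occurs after Day 85". The participant then completes all remaining visits, and for those who do so "the HRCT scan will be performed as scheduled at the Day 183 visit".
- **Table 8-1, footnote 1** covers the same case and says of the early visit: "All assessments planned for the Day 183 visit except for the HRCT scan will be performed". It gives a Day 85 exception only in its separate text on withdrawal from the study. That exception matches Section 9.1.2: "If early EOT falls on or after Day 85 visit, HRCT should also be performed".
- **Sections 4.5 and 8.3.4** set out the imaging plan. Section 4.5 states "Two HRCTs will be performed in this study" and gives about 10 mSv as the maximum total exposure per participant. Section 8.3.4 places the scans at screening and Week 26.

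The footnote refers to 9.1.1 for details, and 9.1.1 refers back to Table 8-1 for the list of assessments, so the cross-references do not settle the matter.

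**The concern.** The footnote and 9.1.1 give opposite instructions for the same visit. A site following the footnote takes one scan after baseline, at Day 183. A site following 9.1.1 as written takes two when treatment stops after Day 85. Either some participants receive a scan that the schedule did not intend, or the maximum exposure in 4.5 is too low for anyone on that path.

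The Day 85 trigger is also defined in two ways. Section 9.1.1 uses the date of discontinuation and requires it to be after Day 85. Footnote 1 (for study withdrawal), 9.1.2 and 9.2 use the date of the early EOT visit and include Day 85 itself. Someone who stops on Day 80 and attends the early visit on Day 90 fails the first test but would meet the second.

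**Working it through.** **Inputs.** Two scans and about 10 mSv (4.5); scans at screening and Week 26 (8.3.4); early EOT visit within 4 weeks, taken as 28 days (9.1.1 and footnote 1); Day 183 visit window of ±5 days (Table 8-1); annual limits of 20 mSv (EU) and 50 mSv (US), and a minimal-risk band of 3 to 50 mSv (4.5). The dose per scan is not stated. I assume the two planned scans are equal.

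**The plan's own count.** Screening (1) + Day 183 (1) = 2 scans, which agrees with 4.5. Implied dose per scan: 10 / 2 = 5 mSv.

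**Participant who stops treatment after Day 85 and continues visits:**

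| Source | Screening | Early EOT | Day 183 | Scans | Approx. dose |
|---|---|---|---|---|---|
| Table 8-1 footnote 1 | 1 | 0 | 1 | 2 | 2 × 5 = 10 mSv |
| 9.1.1 read literally | 1 | 1 | 1 | 3 | 3 × 5 = 15 mSv |

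Ratio to the stated maximum: 15 / 10 = 1.5. The 15 mSv figure is below both annual limits and inside the 3 to 50 mSv band.

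**Spacing of the two post-baseline scans.** Take a stop on Day 141. The early visit falls between Day 141 and Day 141 + 28 = Day 169. Ignoring the visit windows, the gap to the Day 183 scan is between 183 − 169 = 14 days and 183 − 141 = 42 days.

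**When the two visits can coincide.** Section 9.1.1 lets a scheduled visit in window serve as the early EOT visit. The Day 183 window opens on Day 183 − 5 = Day 178. A 28-day limit reaches it only if treatment stops on or after Day 178 − 28 = Day 150. For a stop from Day 86 to Day 149 the early visit, if held on time, is separate from Day 183, and the conflict applies in full.

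**The case against.** The best counter-argument is that 9.1.1 can be read consistently with two scans. Its last HRCT sentence deals specifically with participants who continue visits and refers to a single scan at Day 183. The Day 85 sentence is phrased as a restriction, and could be meant for those who will not return. Section 9.1.1 does allow for such people: after discontinuation, "at a minimum the following data should be collected at clinic visits or via telephone/email contact". On that reading, those who continue visits are handled as the footnote, 4.5 and 8.3.4 imply.

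This reading is plausible, but 9.1.1 does not say that the Day 183 scan replaces the early one, and it expects treatment discontinuers in general to complete their remaining visits. Even on this reading the footnote still conflicts with 9.1.1 for participants followed only by telephone or email, because it excludes the early scan for every treatment discontinuer.

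Several points about size do stand. The affected group is narrow and its number is not estimated. The quantitative HRCT endpoint is exploratory (Protocol Table 2-1), and SAP 2.12 drops exploratory analyses other than soluble biomarkers because of early termination. The scan spacing therefore has no effect on a planned analysis. I could not read the HRCT row of Table 8-1 and have not seen the Imaging Manual named in 8.3.4. Either might give sites a clearer instruction, so divergent practice is a risk and not a certainty.

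**Conclusion.** The inconsistency is real. For treatment discontinuation after Day 85, 9.1.1 and footnote 1 cannot both be followed at the early EOT visit, and a literal reading of 9.1.1 exceeds the stated maximum: three scans against two, or about 15 mSv against about 10 mSv. The dose figure rests on equal doses per scan, and the third scan arises only when the early visit and Day 183 are separate. The risk category in 4.5 does not change, and the primary endpoint, sample size and error rates are untouched. It is still worth correcting. A stated radiation maximum should hold for anyone who follows the protocol as written, and Section 4.1 intends the core text to carry over to later cohorts largely unchanged.

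**What to change.** **Preferred.** Amend 9.1.1 so that participants who stop treatment but continue scheduled visits have no HRCT at the early EOT visit and are scanned only at Day 183. Limit the early scan to participants whose early EOT visit falls on or after Day 85, which is the 9.1.2 trigger, and who will not attend Day 183. Word Table 8-1 footnote 1 the same way. The figure of two scans and about 10 mSv then holds for scheduled imaging.

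**Alternative.** If the sponsor wants both post-baseline scans, bring footnote 1 into line with 9.1.1 and restate 4.5 and 8.3.4 as up to three HRCTs and about 15 mSv.

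In either case, 4.5 should say that its figure excludes imaging prompted by a suspected exacerbation, which 6.7.2.1 allows as chest X-ray or HRCT.

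**Cost.** Only wording changes are needed. Under the preferred option, a participant who intends to attend Day 183 and then does not would have no post-baseline HRCT. Under the alternative, the exposure stated to ethics committees and participants becomes less favourable.
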